The time to first GCA flare after remission (up to Week 52) will be summarized using Kaplan Meier curves. Patients who:

- Withdraw from the study prior to Week 52 will be censored at the time of withdrawal
- Do not have a flare up to Week 52 will be censored at Week 52

Descriptive statistics will also be provided for time to first GCA flare after clinical remission (up to Week 52).

Total cumulative prednisolone dose over 28 and 52 weeks will be summarized over time by treatment group.

The proportion of GCA patients in sustained remission at Week 52 will be analyzed using the methods outlined in Section 9.4.2. Patients who (1) do not achieve remission within 12 weeks of Baseline; or (2) are in the “escape arm”; or (3) drop out from the study prior to/on Week 52, or (4) do not have information to evaluate sustained remission response at Week 52, will be classified as non responders. Patients receiving less than the full amount of prednisolone as required by the taper, e.g. due to missing tablets, will not be classified as non-responders.

The number (and percentage) of patients on prednisolone dose  $\leq$ 5mg/day at Week 19, 28 and 52 will be summarized by treatment group.

The continuous secondary efficacy endpoints (actual value and change from baseline value) will be summarized descriptively by visit (where applicable) and by treatment group.

For SF-36, the following variables will be evaluated:

- SF-36 domain scores

- SF-36 domain score responders
  - Type I responders (improvement of  $\geq 5$  points in  $\geq 6$  domains)
  - Type II responders (improvement of  $\geq 10$  points in  $\geq 3$  domains)
- SF-36 PCS and MCS scores
- SF-36 PCS and MCS score responders
  - Type I responders (improvement of  $\geq 2.5$  points)
  - Type II responders (improvement of  $\geq 5$  points)

The EQ-5D is a questionnaire with 5 questions (regarding mobility, self-care, usual activities, pain/discomfort, and anxiety/depression) each with three categories (no problem, moderate problem, severe problems) and a health state assessment from 0 (worst possible health state) to 100 (best possible health state) (see [Section 6.5.2.1.4](#) for further details). The number and percentage of subjects in each of the three categories for each question will be presented by visit and treatment group. Summary statistics will be provided for the health state assessment by visit and treatment group.

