1.1 Study design

This is a randomized, parallel-group, double-blind, placebo-controlled, multicenter, phase II study designed to evaluate the efficacy of secukinumab compared to placebo in combination with a 26-week prednisolone taper regimen in terms of sustained remission in patients with newly diagnosed or relapsing GCA who are naïve to biological therapy.

The study will consist of 6-week (maximum duration) screening period, a 52-week treatment period and an 8-week safety follow-up period (Figure 1-1).

Figure 1-1 Study design

Patients who do not achieve remission by Week 12, experience a flare after remission or cannot adhere to the prednisolone taper regimen will enter "escape". Upon entering "escape", patients will receive prednisolone at a dose determined by the physician's clinical judgment and continue to receive secukinumab or placebo in a blinded manner. Patients in "escape" should continue to attend all subsequent scheduled visit assessments.

As outlined in the protocol, most flares occurred within the first 6 months in the GiACTA trial (Stone et al 2017). Therefore, the time point for the primary analysis of this study is at Week 28, to evaluate the effect of secukinumab in patients who are on study treatment or placebo for 24 weeks.

At the randomization visit (Baseline) all eligible patients will be given a randomization number that assigns them to one of the following 2 arms in a 1:1 ratio:

- Group 1: secukinumab 300 mg s.c. + 26-week prednisolone taper regimen
- Group 2: placebo s.c. + 26-week prednisolone taper regimen

The patient randomization list was produced by or under the responsibility of Novartis Biometry using a validated system ensuring assignment of treatment arms to randomization numbers in the specified ratio. The randomization scheme was reviewed and approved by a member or delegate of the Novartis Biometry Randomization Group. It is planned to randomize at least 25 patients per treatment group.

Patients will receive secukinumab/placebo at Baseline, Week 1, 2, 3, 4, then every 4 weeks thereafter through to Week 48 (last dose) at the study center. Assessments will be performed in accordance to the study schedule. Patients in both groups will follow the protocol-defined prednisolone taper regimen.

In total, three interim analyses (IAs) will be conducted unless deemed unwarranted by the study team:

- First interim analysis (IA1): after approximately 50% of patients reach Week 28

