1.2 Study objectives and endpoints

The following table (Table 1-1) is an overview of the study objectives and endpoints.

Table 1-1 Study objectives and endpoints

	Objective	Endpoint	
Primary	 To evaluate the efficacy of secukinumab compared to placebo, in combination with a 26- week prednisolone taper regimen, based on the proportion of patients with GCA who have sustained remission. 	 Proportion of GCA patients in sustained remission at Week 28 	

Endpoint Objective To evaluate the efficacy of Remission rate at Week 12 Secondary secukinumab in combination with Time to first GCA flare after Baseline a 26-week prednisolone taper (up to Week 52) regimen versus placebo in patients with GCA, measured by the following: Remission rate at Week 12 Time to first flare after remission Cumulative corticosteroid dose up Total cumulative prednisolone dose to Week 28 and up to Week 52 over 28 weeks and 52 weeks Proportion of patients with GCA Proportion of GCA patients in who have sustained remission sustained remission at Week 52 Proportion of patients on prednisolone Proportion of patients on dose ≤ 5mg/day at Week 19, 28 and prednisolone dose ≤ 5mg/day at Week 19, 28, 52 Changes from baseline in disease Changes from Baseline in disease activity and quality of life measures at activity and quality of life measures at Week 4, 8, 12, 16, Week 4, 8, 12, 16, 20, 24, 28, 36, 44 20, 24, 28, 36, 44 and 52 for each and 52 for each of the following: of the following: Physician's Global Assessment PhGA, VAS (PhGA), Visual Analog Scale (VAS) Patient-reported outcomes (PROs) **PROs** Patient's Global Assessment PGA, VAS (PGA), VAS **FACIT-Fatigue** Functional Assessment of SF-36 Chronic Illness Therapy EQ-5D Fatigue Score (FACIT-Fatigue) Short Form 36 (SF-36) EuroQoL-5D (EQ-5D) Laboratory parameters Change from Baseline in CRP and (Baseline vs. Week 28 and 52): ESR at Week 4, 8, 12, 16, 20, 24, 28, 32, 36, 40, 44, 48, 52 C-reactive protein (CRP) Ervthrocyte sedimentation rate (ESR) To evaluate the safety/ tolerability Safety and tolerability assessments and immunogenicity of over time: incidence and severity of secukinumab in patients with adverse events (AEs) and serious AEs newly diagnosed or relapsing GCA (SAEs)

2 Statistical methods

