2.7.1 Secondary endpoints

The following secondary endpoints will be analyzed:

- Proportion of GCA patients who adhere to the prednisolone taper regimen and are in sustained remission at Week 52
- Remission rate at Week 12
- Time to first GCA flare after Baseline (up to and including Week 52)
- Total cumulative prednisolone dose from start of co-administered treatment to Week 28, 52
- Proportion of patients on prednisolone dose ≤ 5 mg/day at Week 19, 28, 52
- Change from Baseline in PhGA VAS at Week 4, 8, 12, 16, 20, 24, 28, 36, 44 and 52
- Change from Baseline in PGA VAS at Week 4, 8, 12, 16, 20, 24, 28, 36, 44 and 52
- Change from Baseline in FACIT-Fatigue at Week 4, 8, 12, 16, 20, 24, 28, 36, 44 and 52
- Change from Baseline in SF-36 at Week 4, 8, 12, 16, 20, 24, 28, 36, 44 and 52
- Change from Baseline in EQ-5D at Week 4, 8, 12, 16, 20, 24, 28, 36, 44 and 52
- Change from Baseline in CRP (mg/L) at Week 4, 8, 12, 16, 20, 24, 28, 36, 40, 44, 48, 52
- Change from Baseline in ESR (mm/hr) at Week 4, 8, 12, 16, 20, 24, 28, 36, 40, 44, 48, 52

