- Prednisolone dose for GCA will be based on the information collected on the "Dosage Administration Record-Prednisolone" eCRF. However as the prednisolone taper regimen is planned to be 26-weeks in duration, the Investigator is not required to enter daily prednisolone records on the "Dosage Administration Record-Prednisolone" eCRF post Week 26 unless the patient has taken additional prednisolone for GCA. Therefore if the patient is still in the study at the post Week 26 week of interest and has no prednisolone information in the "Dosage Administration Record-Prednisolone" eCRF for that week of interest the patient will be regarded as having 0 mg/day at that week of interest.

Descriptive summary statistics for the change as well as relative change from baseline of PhGA VAS to each study visit of interest will be presented for each treatment group. Change from baseline will only be summarized for patients with both baseline and post baseline values.

The analysis of the PRO secondary endpoints is detailed in Section 2.10.

Descriptive summary statistics for the change from baseline of CRP and ESR to each study visit of interest will be presented for each treatment group. Change from baseline will only be summarized for patients with both baseline and post baseline values. Further details are provided in Section 2.8.3. This analysis will also be presented for the following subgroups:

- Sustained remission until Week 28 (Yes, No)
- Sustained remission until Week 52 (Yes, No)

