2.10 Patient-reported outcomes

The following secondary PRO endpoints will be analyzed according to treatment received (see Section 2.2 for further details) for the FAS:

- Change from Baseline in PGA VAS at Week 4, 8, 12, 16, 20, 24, 28, 36, 44 and 52
- Change from Baseline in FACIT-Fatigue at Week 4, 8, 12, 16, 20, 24, 28, 36, 44 and 52
- Change from Baseline in SF-36 at Week 4, 8, 12, 16, 20, 24, 28, 36, 44 and 52
- Change from Baseline in EQ-5D at Week 4, 8, 12, 16, 20, 24, 28, 36, 44 and 52

Descriptive summary statistics for the change as well as relative change from baseline of PGA VAS to each study visit of interest will be presented for each treatment group. Change from baseline will only be summarized for patients with both baseline and post baseline values.

Descriptive summary statistics for the change as well as relative change from baseline of FACIT-Fatigue to each study visit of interest will be presented for each treatment group. Change from baseline will only be summarized for patients with both baseline and post baseline values.

For SF-36, the following variables will be evaluated:

SF-36 domain scores

- SF-36 domain score responders
 - Type I responders (improvement of ≥ 5 points in ≥ 6 domains)
 - Type II responders (improvement of ≥ 10 points in ≥ 3 domains)
- SF-36 Physical Component Summary (PCS) and Mental Component Summary (MCS) scores (norm-based scores)
- SF-36 PCS and MCS score responders
 - Type I responders (improvement of ≥ 2.5 points)
 - Type II responders (improvement of ≥ 5 points)

Descriptive summary statistics for the change as well as relative change from baseline of SF-36 domain and summary scores to each study visit of interest will be presented for each treatment group. Change from baseline will only be summarized for patients with both baseline and post baseline values. The proportion of responders at each time point will be summarized descriptively for each treatment group.

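### CRP, ESR, PhGA and PRO changes serve a versus-placebo objective but have no between-arm estimate, no baseline adjustment and no stated rule for post-escape values; Week 32 is missing for CRP and ESR

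*SAP*

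**What the plan says.** Protocol Table 2-1 and SAP Table 1-1 place CRP, ESR, PhGA, PGA, FACIT-Fatigue, SF-36 and EQ-5D under a secondary objective that compares secukinumab with placebo.

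**Method.** Protocol 9.5.1 says the continuous secondary endpoints "will be summarized descriptively by visit (where applicable) and by treatment group". The SAP follows this. For the markers, SAP 2.7.2 has "Descriptive summary statistics for the change from baseline of CRP and ESR to each study visit of interest will be presented". For the physician's assessment it has "Descriptive summary statistics for the change as well as relative change from baseline of PhGA VAS to each study visit of interest", and SAP 2.10 has "Descriptive summary statistics for the change as well as relative change from baseline of PGA VAS to each study visit of interest". FACIT-Fatigue and SF-36 are treated like PGA; EQ-5D gets absolute change only. The restriction given with these summaries in SAP 2.7.2 is "Change from baseline will only be summarized for patients with both baseline and post baseline values".

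**Escape.** SAP 1.1 says that on entering escape "patients will receive prednisolone at a dose determined by the" physician, that blinded study drug continues, and that later visits are still attended. SAP 2.7.3 says what escape does to Week 52 sustained remission and Week 12 remission. It says nothing about the continuous measures. The on-treatment filter for laboratory data (SAP 2.8.3 with 2.1.1.4) runs to 84 days after the last study-drug dose and does not stop at escape.

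**Week 32.** SAP 2.7.1 lists "Change from Baseline in CRP (mg/L) at Week 4, 8, 12, 16, 20, 24, 28, 36, 40, 44, 48, 52", and the same weeks for ESR. SAP Table 1-1 lists CRP and "ESR at Week 4, 8, 12, 16, 20, 24, 28, 32, 36, 40, 44, 48, 52".

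**The concern.** There are three gaps.

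First, readers will compare the arms because the objective asks for that comparison. They will find two columns of change scores, with no difference, no interval and no use of the baseline value as a covariate. With about 25 per arm, chance baseline imbalance is not negligible, and baseline itself is measured on 25 to 60 mg/day prednisolone.

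Second, a patient who is a primary-endpoint failure because of escape can contribute a Week 28 CRP taken on investigator-chosen prednisolone, with nothing beside the mean to show it. If escape is more common on placebo and rescue lowers the values, the arm means move closer. The SAP states that its results, and the Week 52 data in particular, are to inform a Phase III program, so an unlabelled table could be read as absence of effect.

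Third, two parts of the SAP disagree on whether Week 32 is an analysis visit for CRP and ESR.

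**Working it through.** **The plan's own figures.** The plan gives no SD, correlation, escape rate or target difference for these measures. Its only design figures concern the primary endpoint. The first row of SAP Table 3-1 (14/25 versus 4/25) reproduces: posterior median difference 0.378 against 0.38 stated. That does not bear on this point. The sizes below therefore rest on labelled assumptions.

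**1. Gain from baseline adjustment.** Let r be the correlation of baseline with follow-up, and assume equal variances (set to 1).
- Change-score variance: 2(1 − r).
- ANCOVA residual variance: 1 − r².
- Ratio: (1 − r²) / [2(1 − r)] = (1 + r)/2.

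| r (assumed) | variance ratio | interval-width ratio | narrower by |
|---|---|---|---|
| 0.3 | 0.65 | 0.81 | 19% |
| 0.5 | 0.75 | 0.87 | 13% |
| 0.7 | 0.85 | 0.92 | 8% |

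Equal variances are doubtful for CRP and ESR, given baseline prednisolone. The direction does not depend on that assumption. With SDs s_x at baseline and s_y at follow-up, change-score variance minus ANCOVA variance is s_x² + s_y² − 2r·s_x·s_y − s_y²(1 − r²) = (s_x − r·s_y)², which cannot be negative. The small cost of estimating one slope is ignored here.

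**2. Chance imbalance.** With 25 per arm, the standard error of the baseline difference is √(2/25) = 0.28 SD. An imbalance of that size moves a change-score difference by (1 − r) × 0.28: about 0.20, 0.14 and 0.08 SD for r = 0.3, 0.5 and 0.7.

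**3. What rescue could do.** SAP 2.5.2 expects response rates of 56% and 18%, so non-response is 44% and 82% (0.44 × 25 = 11 and 0.82 × 25 = 20.5 patients). This is an upper bound for escape, because non-response also covers treatment discontinuation, missing information and taper non-adherence. Suppose active disease shifts a measure by D and rescue removes a fraction f of that shift. The gap between arms is then (share on placebo − share on secukinumab) × D × (1 − f).

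| share with active disease | f = 0 | f = 0.5 | f = 0.8 | f = 1 |
|---|---|---|---|---|
| all non-responders (0.82 v 0.44) | 0.38D | 0.19D | 0.08D | 0 |
| half of them (0.41 v 0.22) | 0.19D | 0.10D | 0.04D | 0 |

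At the SAP's minimal effect (40% versus 18%), the first entry would be (0.82 − 0.60)D = 0.22D. The direction follows if placebo patients escape more often and rescue works. The size is open, since D, f and the escape shares are all assumed.

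**4. Would excluding post-escape values help?** Under the same model, if all non-response came through escape, exclusion would leave 0.56 × 25 = 14 and 0.18 × 25 = 4.5 patients at Week 28, all without active disease. The difference would then be zero by construction. Exclusion selects on a post-randomization event and pushes the arms together itself.

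**5. Week 32.** SAP Table 1-1, Protocol Table 2-1 and Protocol 9.5.1 include it, and Protocol Table 6-1 schedules both tests at that visit. SAP 2.7.1 omits it. SAP Section 4 lists three changes from the protocol, and this is not one of them.

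**The case against.** The best defence is that this is a 50-patient Phase II trial, that the protocol itself prescribes descriptive summaries, and that nothing formal depends on them. There is no key secondary objective, and the GO criteria use only the primary risk difference. Keeping post-escape values is a recognised treatment-policy choice. Rescue is also visible elsewhere: cumulative prednisolone to Weeks 26, 28 and 52, the proportion at or below 5 mg/day, average daily dose by taper week, and reasons for non-response. CRP and ESR are additionally split by sustained remission, which places escape patients in the No group. The worst-record rule in SAP 2.1.1.12 may keep some flare values within a visit window.

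Most of this stands, and it limits the point to reporting. It does not supply an estimate for a stated comparative objective. The prednisolone tables do not give the number in escape at each visit. The remission split covers CRP and ESR only, conditions on an outcome defined partly by those two markers, and mixes escape with other failures. The worst-record rule cannot recover an unrescued value at later visits.

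A reader might infer three stronger things that the documents do not support:
- **That baseline is ignored.** It is subtracted, and four measures also get relative change. What is missing is covariate adjustment.
- **That rescue will hide a real effect.** No escape rate or size of rescue effect is given.
- **That post-escape values do not belong in the tables.** They are legitimate if the summary is labelled, and simple exclusion is worse, as step 4 shows.

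**Conclusion.** The point holds as a gap in estimation and labelling. Seven measures serving a versus-placebo objective have no between-arm estimate, no interval and no baseline adjustment, and the handling of post-escape values is left unstated. The Week 32 omission is a separate, plain inconsistency and adds no weight to the escape argument.

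The quantified part is the precision gain: intervals about 8 to 19% narrower than for an unadjusted difference in change scores, assuming equal variances and a correlation of 0.3 to 0.7. The plan produces neither interval, so this is a reason to choose the adjusted version when one is added. Narrowing of the arm difference through rescue is plausible in direction and unquantified in size. No formal conclusion of the trial is affected.

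**What to change.** 1. In SAP 2.7.2 and 2.10, add for each measure a baseline-adjusted secukinumab-minus-placebo difference with 95% CI at Weeks 12, 28 and 52, from ANCOVA or a repeated-measures model. Label it as supportive and record the addition in SAP Section 4. Keep the descriptive tables.
2. State in SAP 2.7.3 that these summaries and estimates include values after escape (treatment policy), and say so in the table titles.
3. Print the number in escape by arm and visit beside these tables.
4. Restore Week 32 for CRP and ESR in SAP 2.7.1.
5. Do not add a display that simply drops post-escape values.

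The cost is SAP text and a few extra tables from data already collected, with no change to trial conduct. The intervals would be supportive and unadjusted for multiplicity, and should be described that way.

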2.7.3 Handling of missing values/censoring/discontinuations

For sustained remission until Week 52, patients will be classified as non-responders if they fulful any of the following:

- Do not achieve remission within 12 weeks of Baseline
 - Note: Remission refers to the absence of flare.
- Are in the "escape arm"
 - Note: This refers to the patient entering escape between Baseline and Week 52.
- Prematurely discontinue study treatment prior to Week 52
 - Note: Absence of flare is checked prior to study treatment administration.
- Do not have information to evaluate sustained remission response until Week 52

Patients receiving less than the full amount of prednisolone for GCA as required by the taper, e.g. due to missing tablets, will not be classified as non-responders with the exception of those who are classified as non-adherent to the prednisolone taper regimen (refer to Section 2.5.1 for definition of adherence to the prednisolone taper regimen). Note: The final decision on whether

the patient is non-adherent to the prednisolone taper will be confirmed by the blinded medical team on a by-patient basis in a BDRM prior to CDBL. This decision will be documented in the associated BDRM minutes.

For remission rate at Week 12, patients will be classified as non-responders if they fulfil any of the following:

- Prematurely discontinue study treatment
- Enter "escape" therapy

Note: Patients will be classified as non-responders for the above two scenarios from the point of withdrawal/escape onwards. Patients with a missing remission status at Week 12 will be classified as non-responders.

For time to first GCA flare after remission (up to and including Week 52), patients who:

- Prematurely discontinue study treatment prior to Week 52 will be censored at the time of premature discontinuation
- Complete treatment and do not have a flare will be censored at their last visit in the treatment phase

2.8 Safety analyses

Patients will be analyzed according to treatment received (see Section 2.2 for further details) for the Safety Set.

2.8.1 Adverse events

Adverse events will be coded by primary SOC and PT according to the MedDRA version 23.0 or later and will be presented for the whole study period. Only treatment emergent AEs (TEAEs) will be summarized.

Treatment emergent AEs are defined as events started after the first dose of study treatment or events present prior to the first dose of study treatment but increased in severity after dosing based on preferred term and within last dose + 84 days. For handling of missing or incomplete start and end dates, refer to Section 5.1.2.

Treatment emergent AEs will be summarized for each treatment group by presenting the crude incidence of patients having any TEAE and having a TEAE by primary SOC and by PT. Patients who experienced multiple AEs for a PT will be counted once for that PT, similarly for patients with multiple AEs per primary SOC. For summaries of TEAEs by severity, if a patient reports more than one AE with the same PT, only the AE with the maximum severity will be counted. Similarly, if a patient reports more than one AE within the same primary SOC, the event with the maximum severity will be counted for the SOC level. If the severity of a particular AE is missing, this severity will be treated as missing in summaries and listed accordingly.

The following TEAE information will be summarized separately by contingency tables:

- Adverse events, regardless of relationship to study or co-administered prednisolone treatment, by primary SOC and PT
- Adverse events, suspected to be related to study treatment, by primary SOC and PT

- Adverse events, suspected to be related to co-administered prednisolone treatment, by primary SOC and PT
- Serious AEs, regardless of relationship to study or co-administered prednisolone treatment, by primary SOC and PT
- Serious AEs, suspected to be related to study treatment, by primary SOC and PT
- Serious AEs, suspected to be related to co-administered prednisolone treatment, by primary SOC and PT
- Adverse events, regardless of relationship to study or co-administered prednisolone treatment, by primary SOC, PT and maximum severity (mild, moderate, severe)
- Adverse events leading to study treatment discontinuation, regardless of relationship to study or co-administered prednisolone treatment, by primary SOC and PT
- Adverse events leading to study treatment discontinuation, suspected to be related to study treatment, by primary SOC and PT
- Adverse events leading to study treatment discontinuation, suspected to be related to co-administered prednisolone treatment, by primary SOC and PT
- Adverse events requiring study dose adjustment/interruption, regardless of relationship to study or co-administered prednisolone treatment, by primary SOC and PT
- Adverse events requiring additional therapy, regardless of relationship to study or co-administered prednisolone treatment, by primary SOC and PT

In addition, for the legal requirements of clinicaltrials.gov and EudraCT, 2 required tables on TEAEs which are not SAEs with an incidence greater than 5% and on treatment emergent SAEs and SAEs suspected to be related to study treatment will be provided by primary SOC and PT.

If for the same patient, several consecutive AEs (irrespective of study treatment causality, seriousness and severity) occurred with the same primary SOC and PT:

- A single occurrence will be counted if there is ≤ 1 day gap between the end date of the preceding AE and the start date of the consecutive AE
- More than one occurrence will be counted if there is > 1 day gap between the end date of the preceding AE and the start date of the consecutive AE

For occurrence, the presence of at least one SAE/SAE suspected to be related to study treatment/non-SAE has to be checked in a block e.g., among AEs in a \leq 1 day gap block, if at least one SAE is occurring, then one occurrence is calculated for that SAE.

